### 11.3. Appendix 3: Assessment Windows

#### 11.3.1. Definitions of PK Assessment Windows

Analysis Set / Domain	Target / nominal time	Target Window		Analysis Timepoint
		Beginning Timepoint	Ending Timepoint	
PK Concentration (analyte is GSK3008356)	Pre-Dose	within 30 mins of dosing	dosing time	0 Hours
	0.25 hour	00:13	00:17	Actual draw time
	0.5 hour	00:27	00:33	Actual draw time
	1 hour	00:57	01:03	Actual draw time
	1.5 hours	01:27	01:33	Actual draw time
	All Subsequent draws between 2 hours – 24 hours*	Target – 00:10	Target + 00:10	Actual draw time
	All Subsequent draws between 36 hours – 72 hours*	Target – 00:30	Target + 00:30	Actual draw time

**NOTES :**

- Any actual draws outside of these time windows will be listed as deviations (not necessarily “important”), but will still be used in the concentration assay and determination of PK parameters according to the actual draw time.
- Any concentrations determined from blood draws inside or outside these windows may still be excluded from PK determinations for other reasons, such as sample handling or other protocol deviations.
- \* All Subsequent draws after 2 hour will be at hours 4, 6, 8, 12, 18, 24, 36, 48, and 72 in Part 1.
- In Part 2, All Subsequent draws after 2 hour will be at hours 4, 6, 8, 12, and 18 on Day 1; then PK Samples will be taken at Pre-Dose on Days 2, 4, 5, 6, 12, and 13 only during period Days 2-13 Morning Dose; and starting on Day 14, PK Samples will be taken at Pre-dose, hours at 0.25, 0.5, 1, 1.5, 2, 4, 6, 8, 12, 18, 24, 36, 48, and 72.

### 11.3.2. Definitions of Triglyceride (Postprandial) Assessment Windows

Analysis Set / Domain	Target / nominal time		Target Window		Analysis Timepoint
	Rel to Dosing	Rel to Meal	Beginning Timepoint	Ending Timepoint	
Triglyceride	+01:00	-01:00	Target – 00:15	Target + 00:15	-01:00
	+02:00	00:00	Target – 00:15	Target + 00:15	00:00
	+03:00	+01:00	Target – 00:15	Target + 00:15	+01:00
	+04:00	+02:00	Target – 00:15	Target + 00:15	+02:00
	+05:00	+03:00	Target – 00:15	Target + 00:15	+03:00
	+06:00	+04:00	Target – 00:15	Target + 00:15	+04:00
	All Subsequent assessments (7, 8, 9, 12 hours post-dose or 5, 6, 7, 10 hours post-meal)		Target – 00:15	Target + 00:15	Nominal Time relative to meal

**NOTES :**

- For evening dosing regimens, triglyceride assessments will be at the same times relative to the meal, but the meal will be the following morning (not at 2 hours post-dose as with morning dosing).
- Any triglyceride assessments outside of these time windows will be listed as deviations (not necessarily "important"), but will still be used in the analysis. However, any evaluation which is closer to an adjacent (nominal) time than to its own nominal sampling will not be used.
- Any triglyceride assessments inside or outside these windows may still be excluded for other reasons, such as sample handling or other protocol deviations.
- Part 1: The assessment will be on Day -1 and Day 1; Part 2: The assessment will be on Day -1, Day 1 and Day 14. On Day -1, Target/nominal time is only relative to fat meal.

### 11.3.3. Definitions of Vital Signs and ECG Assessment Windows

Analysis Set / Domain	Target / nominal time	Target Window		Analysis Timepoint
		Beginning Timepoint	Ending Timepoint	
Vital Signs (BP, HR, pulse, Temp.)* and 12-Lead ECG	Screening	Within 28 day	Day -1	Screening
	Checking in	Day -1	Day -1	Day -1
	Pre-Dose	Within 12 hours before dosing	dosing time	00:00
	1 Hour Post-Dose	Target – 00:15	Target + 00:15	+01:00
	4 Hours Post-Dose	Target – 00:15	Target + 00:15	+04:00
	12 Hours Post-Dose	Target – 00:15	Target + 00:15	+12:00

**NOTES :**

- There are also 24-hour assessments of these shown in the protocol. In cases of repeat dose (Part 2), these serve as the pre-dose assessment on the next day. In other cases, they (and 48 and 72 hours) are follow-up assessments on subsequent days, in which case, the target window will be ± 6 hours, but the assessments will be used if they occur on that day.
- \*: Temperature Screening and Day -1 only.

- 
- ECG: Assessment windows are same as those of Vital Signs excluding time points at Checking in (Day -1), 48 hours, and follow-up (Days 6-8) for Part 1
  - Any assessments outside of these time windows will be listed as deviations (not necessarily "important"), but will still be used in the analysis. However, any evaluation which is closer to an adjacent (nominal) time than to its own nominal sampling will not be used

## 11.4. Appendix 4: Treatment States and Phases

### 11.4.1. Treatment Phases

Assessments and events will be classified according to the time of occurrence relative to start and/or stop date of the study treatment in double-blind phase I study.

Treatment Phase	Definition
Pre-Treatment	Date $\leq$ Study Treatment Start Date
On-Treatment	Study Treatment Start Date < Date $\leq$ Study Treatment Stop Date
Post-Treatment	Date > Study Treatment Stop Date

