6.3.1.3. Follow-up of AEs and SAEs

After the initial AE/SAE report, the investigator is required to proactively follow each subject at subsequent visits/contacts. All SAEs, and non-serious AEs of special interest (as defined in Section 3.5.1) will be followed until resolution, until the condition stabilizes, until the event is otherwise explained, or until the subject is lost to follow-up (as defined in Section 4.5). Further information on follow-up procedures is given in Section 11.3.

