#### 11.4.2.1. Treatment States for AE Data

Treatment State	Definition
Pre-Treatment	AE Start Date < Study Treatment Start Date
On-Treatment	If AE onset date is on or after treatment start date & on or before treatment stop date. Study Treatment Start Date $\leq$ AE Start Date $\leq$ Study Treatment Stop Date
Post-Treatment	If AE onset date is after the treatment stop date. AE Start Date > Study Treatment Stop Date
Onset Time Since 1 st Dose (Days)	If Treatment Start Date > AE Onset Date = AE Onset Date - Treatment Start Date If Treatment Start Date $\leq$ AE Onset Date = AE Onset Date - Treatment Start Date + 1 Missing otherwise.
Duration (Days)	AE Resolution Date – AE Onset Date + 1
Drug-related	If relationship is marked 'YES' on eCRF.

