## 11.5. Appendix 5: Data Display Standards & Handling Conventions

### 11.5.1. Study Treatment & Sub-group Display Descriptors

Part 1: All treatments are dosed in the morning; some regimens are single morning dosing while other regimens are multiple dosing.

Part 2: All treatments are dosed in the morning repeated over 14 days. All doses are BID.

Consistent with the treatment group code shown in the randomization schedules, parts, cohorts, actual doses, and treatment regimens will appear as follows in data displays produced:

Treatment Group Descriptions			
RandAll NG		Data Displays for Reporting	
Code	Description	Description	Order 
Part 1			
A1	SD Cohort 1 GSK3008356 Active	5mg	2
A2	SD Cohort 2 GSK3008356 Active	10mg	3
A3	SD Cohort 3 GSK3008356 Active	30mg	4
A4	SD Cohort 4 GSK3008356 Active	75mg	5
A5	SD Cohort 5 GSK3008356 Active	200mg	6
A6	SD Cohort 6 GSK3008356 Active	125mg	7
A7	MD Cohort 7 GSK3008356 Active	100mg t0, t4	8
A8	MD Cohort 8 GSK3008356 Active	100mg t0, t16	9
A9	SD Cohort 9 GSK3008356 Active	cancelled	n/a
A10	MD Cohort 10 GSK3008356 Active	10mg q1h x 9	10
A11	MD Cohort 11 GSK3008356 Active	5mg q1h x 9	11
P1	Placebo	Placebo	1
Part 2			
B1	RD Cohort 1 GSK3008356 Active (AM) 14 days dosing	10mg BID	2
B2	RD Cohort 2 GSK3008356 Active (PM) 14 days dosing	1mg BID	3

Treatment Group Descriptions			
RandAll NG		Data Displays for Reporting	
Code	Description	Description	Order [1]
B3	RD Cohort 3 GSK3008356 Active (PM) 14 days dosing	3mg BID	4
P2	RD Placebo 14 days dosing	Placebo	1

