#### 11.7.2.1. Handling of Missing Dates

Element	Reporting Detail
General	Partial dates will be displayed as captured in subject listing displays.
Adverse Events	
 
• The eCRF allows for the possibility of partial dates (i.e., only month and year) to be recorded for AE start and end dates; that is, the day of the month may be missing. In such a case, the following conventions will be applied for calculating the time to onset and the duration of the event: 
 
○ Missing Start Day: First of the month will be used unless this is before the
 
 
 

Element	Reporting Detail
	
start date of study treatment; in this case the study treatment start date will be used and hence the event is considered On-treatment as per: Appendix 4 –Treatment States and Phases.
 
 
○ Missing Stop Day: Last day of the month will be used, unless this is after the stop date of study treatment; in this case the study treatment stop date will be used.
 
● Completely missing start or end dates will remain missing, with no imputation applied. Consequently, time to onset and duration of such events will be missing.
 
● Start or end dates which are completely missing (i.e. no year specified) will remain missing, with no imputation applied.
 

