**11.7.2.2. Handling of Partial Dates**

Element	Reporting Detail
Concomitant Medications	
 
● Partial dates for any concomitant medications recorded in the CRF will be imputed using the following convention: 
 
○ If the partial date is a start date, a '01' will be used for the day and 'Jan' will be used for the month
 
○ If the partial date is a stop date, a '28/29/30/31' will be used for the day (dependent on the month and year) and 'Dec' will be used for the month.
 
 
 
● The recorded partial date will be displayed in listings.
 

Adverse Events	
 
● Any partial dates for adverse events will be raised to data management. If the full date cannot be ascertained, the following assumptions will be made: 
 
○ If the partial date is a start date, a '01' will be used for the day and 'Jan' will be used for the month.
 
○ However, if these results in a date prior to Week 1 Day 1 and the event could possibly have occurred during treatment from the partial information, then the Week 1 Day 1 date will be assumed to be the start date.
 
○ The AE will then be considered to start on-treatment (worst case).
 
○ If the partial date is a stop date, a '28/29/30/31' will be used for the day (dependent on the month and year) and 'Dec' will be used for the month.
 
 
 
● The recorded partial date will be displayed in listings.
 

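### Do the treatment-phase boundary in SAP 11.4.1 and the capped adverse-event stop date in SAP 11.7.2.1 distort any planned result?

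*SAP*

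**What the plan says.** **Treatment phases.** SAP 11.4.1 classes any date up to and including the treatment start date as pre-treatment. It defines on-treatment as "Study Treatment Start Date < Date $\leq$ Study Treatment Stop Date". SAP 11.4.2.1, which applies to adverse events (AEs) only, includes the start date: "If AE onset date is on or after treatment start date & on or before treatment stop date".

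**Missing AE stop day.** Two sections cover the same field.

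- SAP 11.7.2.1: "Last day of the month will be used, unless this is after the stop date of study treatment", in which case the treatment stop date is used instead. The stated purpose is that "the following conventions will be applied for calculating the time to onset and the duration of the event".
- SAP 11.7.2.2: "Any partial dates for adverse events will be raised to data management". If the full date still cannot be found, the stop day is set to month-end, "dependent on the month and year) and 'Dec' will be used for the month". There is no cap at treatment stop.

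AE duration is defined in SAP 11.4.2.1 as resolution date minus onset date plus 1.

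**The concern.** Read literally, the two tables in SAP Appendix 4 put the same day in opposite phases. Post-dose vital signs, ECGs and triglyceride samples on Day 1 would be labelled pre-treatment. Where all doses fall on one date, no date at all would be on treatment.

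The stop-date cap looks worse because it can produce an impossible value. Protocol 6.3.1.1 collects AEs until the follow-up contact, which is Day 6-8 in Part 1 and Day 20-22 in Part 2. Events starting after the last dose are therefore expected. For such an event with a missing stop day, the capped stop falls before the onset. An event that starts on treatment and outlasts it would be cut at the last dose. Gastrointestinal tolerability decided whether the study went on to Part 3, so if AE durations fed that assessment or the report, the error would matter.

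**Working it through.** The plan states no figure on this point, so I applied the rules as written.

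**1. Phase boundary.** Let S be the treatment start date and E the treatment stop date.

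- One-date dosing, S = E: the set of dates later than S and no later than E is empty, so 11.4.1 gives 0 on-treatment dates and 11.4.2.1 gives 1. From the regimens in SAP 11.5.1, this covers Part 1 Cohorts 1-7, 10 and 11. Cohort 8 depends on whether its 16h dose passes midnight, and Cohort 9 was cancelled.
- Dosing over 14 dates: 11.4.1 gives 13 on-treatment dates and 11.4.2.1 gives 14.

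**2. AE duration with a missing stop day and a fully known onset.** Let onset be E + k with k ≥ 1. Month-end of the resolution month is then always after E, so the cap always applies:

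duration = E − (E + k) + 1 = 1 − k.

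This gives 0 for k = 1, −2 for k = 3 and −7 for k = 8. Run over 730 start dates, 1- and 14-day treatment, k from 1 to 8 and resolution 0 to 60 days after onset (730 × 2 × 8 × 61 = 712,480 cases), the result was never above 0. Month-end without the cap was never below 1.

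| Assumed dates | 11.7.2.1 | 11.7.2.2 |
|---|---|---|
| Dose 10 June, onset 12 June, stop in June | 10 − 12 + 1 = −1 | 30 − 12 + 1 = 19 |
| Last dose 14 May, onset 13 May, true stop 20 May (8 days) | 14 − 13 + 1 = 2 | 31 − 13 + 1 = 19 |

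In the second row neither rule recovers the true length; one understates it and the other overstates it.

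If the onset day is missing too, 11.7.2.1 moves onset back to the first of the month or to treatment start. The duration was then positive in 4,976 of 5,840 cases tried.

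For Part 2 the value of E depends on clock time. SAP 11.5.1 says "All treatments are dosed in the morning repeated over 14 days. All doses are BID", and the second dose is at 16h. A first dose at 08:00 or later puts the last dose on Day 15 rather than Day 14 and shifts the results by one day.

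**3. Where these variables could reach a planned result.**

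- Baselines: SAP 11.5.2.1 fixes them by named time point (Day 1 pre-dose, or Day −2/Day −1), not by phase.
- Triglycerides: SAP 8.2.1.1 and 8.2.1.2 compare Day 1 and Day 14 with Day −1 by nominal time.
- Values of potential clinical importance: SAP 7.1.3.1 and 7.1.3.2 count any post-baseline value.
- AE tables: SAP 7.1.1.1 counts subjects and draws no line between pre-treatment and treatment-emergent events.
- Exposure: SAP 11.6.2 uses stop − start + 1, which includes the start date.
- Displays: no title in Appendix 12 names treatment phase or AE duration. SAP 11.7.2.1 and 11.7.2.2 both show partial AE dates in listings as recorded.

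None of these uses the 11.4.1 phases or an imputed AE stop date.

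**The case for a change.** The strongest case for a change is that a specified derivation should never return an impossible value. AE duration is specified, two sections impute the same field differently, and neither is given precedence. SAP 2.2 reports that 6 of 8 subjects in Part 2 Cohort 1 were withdrawn early for gastrointestinal issues. An event there that outlasted dosing and lacked a stop day would be cut at the last dose. The rewording would be cheap.

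The inconsistency stands, but its practical force does not.

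- SAP 11.7.2.2 is the section that sends partial AE dates to query and says what to do if the query fails. An analyst following it uses month-end and never gets a duration below 1. The impossible value needs the query step from one section and the imputation from the other.
- A further reading, that December replaces a known month, would stretch the June example to 203 days. It is not tenable. The day is made to depend on the month and year, which would be pointless if the month were always December.
- The two phase tables cover different data. AE collection begins after the first dose, so Day 1 belongs on treatment for AEs. For vital signs, ECGs and serum lipids, Day 1 also holds the pre-dose baseline. Any date-only rule must misplace part of Day 1, and the 11.4.1 rule keeps the baseline pre-treatment. Copying the AE rule would put it on treatment. A date-and-time rule would sort Day 1 correctly but would no longer match the date-only AE table.
- The Cohort 1 withdrawals enter the AE and withdrawal tables whatever duration is derived.
- A replacement stop rule needs its own judgement. Protocol 6.3.1.3 says "All SAEs, and non-serious AEs of special interest (as defined in Section 3.5.1) will be followed until resolution", with alternatives such as stabilisation, while ordinary AEs are collected only to the follow-up contact. No single cap suits both.
- SAP 11.7.2.3 rules out imputation, but for statistical analysis. It does not settle which AE date rule applies.

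**Conclusion.** No change is called for. The phase boundary in SAP 11.4.1 and the cap in SAP 11.7.2.1 are slips of drafting, and the arithmetic against them is right: 0 on-treatment dates for one-date dosing, and 1 − k days for a known onset k days after treatment stop. Neither reaches a baseline, an AE incidence, an exposure figure or a triglyceride or laboratory summary, so correcting them would improve no stated estimate, precision, bias or safety conclusion. An analyst would resolve the overlap sensibly by following SAP 11.7.2.2 for dates that remain unknown after query.

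This rests on two assumptions. The first is that Appendix 12 titles reflect display content. The standard shells are not reproduced, so a duration column in an AE listing cannot be excluded, but the recorded partial date would be listed as captured. The second is that unresolved AE stop days are few. Their number is not given. Subjects stay in the unit to Day 4 in Part 1 and Day 17 in Part 2, and partial dates are queried, so it may be zero.

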### 11.4.2. Treatment States

Assessments and events will be classified according to time of occurrence relative to the start and/or stop date of the study treatment.

#### 11.4.2.1. Treatment States for AE Data

Treatment State	Definition
Pre-Treatment	AE Start Date < Study Treatment Start Date
On-Treatment	If AE onset date is on or after treatment start date & on or before treatment stop date. Study Treatment Start Date $\leq$ AE Start Date $\leq$ Study Treatment Stop Date
Post-Treatment	If AE onset date is after the treatment stop date. AE Start Date > Study Treatment Stop Date
Onset Time Since 1 st Dose (Days)	If Treatment Start Date > AE Onset Date = AE Onset Date - Treatment Start Date If Treatment Start Date $\leq$ AE Onset Date = AE Onset Date - Treatment Start Date + 1 Missing otherwise.
Duration (Days)	AE Resolution Date – AE Onset Date + 1
Drug-related	If relationship is marked 'YES' on eCRF.

#### NOTES:

- If the study treatment stop date is missing then the AE will be considered to be On-Treatment.

## 11.5. Appendix 5: Data Display Standards & Handling Conventions

### 11.5.1. Study Treatment & Sub-group Display Descriptors

Part 1: All treatments are dosed in the morning; some regimens are single morning dosing while other regimens are multiple dosing.

Part 2: All treatments are dosed in the morning repeated over 14 days. All doses are BID.

Consistent with the treatment group code shown in the randomization schedules, parts, cohorts, actual doses, and treatment regimens will appear as follows in data displays produced:

Treatment Group Descriptions			
RandAll NG		Data Displays for Reporting	
Code	Description	Description	Order 
Part 1			
A1	SD Cohort 1 GSK3008356 Active	5mg	2
A2	SD Cohort 2 GSK3008356 Active	10mg	3
A3	SD Cohort 3 GSK3008356 Active	30mg	4
A4	SD Cohort 4 GSK3008356 Active	75mg	5
A5	SD Cohort 5 GSK3008356 Active	200mg	6
A6	SD Cohort 6 GSK3008356 Active	125mg	7
A7	MD Cohort 7 GSK3008356 Active	100mg t0, t4	8
A8	MD Cohort 8 GSK3008356 Active	100mg t0, t16	9
A9	SD Cohort 9 GSK3008356 Active	cancelled	n/a
A10	MD Cohort 10 GSK3008356 Active	10mg q1h x 9	10
A11	MD Cohort 11 GSK3008356 Active	5mg q1h x 9	11
P1	Placebo	Placebo	1
Part 2			
B1	RD Cohort 1 GSK3008356 Active (AM) 14 days dosing	10mg BID	2
B2	RD Cohort 2 GSK3008356 Active (PM) 14 days dosing	1mg BID	3

Treatment Group Descriptions			
RandAll NG		Data Displays for Reporting	
Code	Description	Description	Order [1]
B3	RD Cohort 3 GSK3008356 Active (PM) 14 days dosing	3mg BID	4
P2	RD Placebo 14 days dosing	Placebo	1

**NOTES:**

- General order (left-right or top-down) of treatments being presented in TFLs, as appropriate. Since displays will be separate for the 2 parts of the study, outputs will contain only those doses/regimens used in that part.

**11.5.2. Baseline Definition & Derivations****11.5.2.1. Baseline Definitions**

Parameter				Baseline Used in Data Display
	Screening (within 28 days)	Day -2, Day -1 [1]	Day 1 (Pre-Dose)	
Part 1 – Single Dose				
Vital Signs (BP, HR, pulse)	X	X	X	Day 1 (Pre-Dose)
Hematology, Chemistry	X	X		Day -2, Day -1
UA	X	X		Day -2, Day -1
12-Lead ECG	X		X	Day 1 (Pre-Dose)
Exploratory PD Labs (Serum Lipid Levels)	X		X	Day 1 (Pre-Dose)
Part 2 – Repeat Dose				
Vital Signs (BP, HR, pulse)	X	X	X	Day 1 (Pre-Dose)
Hematology, Chemistry	X	X		Day -2, Day -1
UA	X	X		Day -2, Day -1
12-Lead ECG	X		X	Day 1 (Pre-Dose)
Exploratory PD Labs (Serum Lipid Levels)	X		X	Day 1 (Pre-Dose)

**NOTES :**

- Unless otherwise stated, the mean of replicate assessments at any given time point will be used as the value for that time point.
- [1]: Based on logistics, Day -1 assessments may occur on Day -2.

All TG collection is relative to nominal or actual dose time 0h. For postprandial TG assessments, Day -1 is the Baseline TG Excursion since no study drug was administered. Day 1 and Day 14 are Post-Dose TG Excursion responses. Within these TG Excursions, times 1h and 2h are pre-meal. The challenge meal is administered at 2h (after lab collection). Times 3h onward are post-meal (postprandial) TG Excursion. See the Tables in Section 11.2.1.2 and Section 11.2.1.6.

Keep in mind that the 3h (post dose) TG collection is 1h post-meal (postprandial) whether on Baseline Day or Post-Dose Day. However, the labelling of the data point should remain relative to dosing (3h) and not changed to be relative to meal.

As noted in Section 8.2, one Part 1 and all three Part 2 cohorts had a second (20% fat) meal provided at 6h post-dose.

**11.5.2.2. Derivations and Handling of Missing Baseline Data**

Derivation	How Derived	Handling of Missing Data
Change from Baseline	= Post-Dose Visit Value – Baseline	Missing if either baseline or post is missing
%Change from Baseline	= (Post-Dose Visit Value – Baseline)/Baseline	Missing if either baseline or post is missing
Log Transformation	= [natural] log (PK Parameter)	Missing if PK parameter is missing
Back-Transformation	= EXP(estimate or confidence limit)	Missing if estimate or CL is missing
Maximum LFT	= maximum of that LFT (e.g., ALT) value for that subject over time	Missing only if all values of that LFT are missing for that subject
%AUC ex	= [AUC(0-inf) – AUC(0-t)] / AUC(0-inf) x 100	Missing if AUC(0-inf) is missing
Accumulation Ratio (R 0 )	= [AUC 0-τ on the final day (steady state)] / [AUC 0-τ on Day 1]	Missing if AUC 0-τ is missing for either Day 1 or final day
Accumulation Ratio (R s )	= [AUC 0-τ on the final day (steady state)] / [AUC 0-inf on Day 1]	Missing if either AUC 0-τ on final day or AUC(0-inf) on Day 1 is missing.
Corrected by adding the adjusting value to post dose TG values	
 
• Part 1 Day 1 Correction:                             
 
○ (Day -1 (1hr + 2hr)/2) – (Day 1 (1hr + 2hr)/2)
 
 
 
• Part 2:                             
 
○ Day 1 Correction:                                     
 
❖ (Day -1 (1hr + 2hr)/2) –
 
 
 
 
 
	Missing if any TG value is missing for either post dose or pre-dose at any time point

Derivation	How Derived	Handling of Missing Data
	
(Day 1 (1hr + 2hr)/2)
 
 
○ Day 14 Correction:                             
 
❖ (Day -1 (1hr + 2hr)/2) – (Day 14 (1hr + 2hr)/2)
 
 
 
	

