## 4. ANALYSIS POPULATIONS

Population	Definition / Criteria	Analyses Evaluated
Screened	
 
Comprised of all subjects who were screened including subjects with screen failure.
 
	
 
Study Disposition
 

Enrolled	
 
Comprised of all subjects who consented and were screened with eligibility verified.
 
	
 
Study Population
 

Safety:	
 
Comprised of all subjects who receive at least one dose of study medication.
 
This population will be based on the treatment/dose the subject actually received.
 
	
 
Study Population
 
Safety
 
Bristol Stool Form Scale
 
Exploratory PD Markers
 

PKC: PK Concentration	
 
Comprised of subjects for whom a pharmacokinetic sample was obtained and analysed.
 
This population will be based on the treatment/dose the subject actually received.
 
	
 
Analysis of PK Concentrations
 

PKP: PK Parameter	
 
Comprised of all subjects in the PKC population who receive at least one active dose of GSK3008356 and provide pharmacokinetic parameters.
 
This population will be based on the treatment/dose the subject actually received.
 
	
 
Analysis of PK Parameters
 
PK/PD
 

PD	
 
Comprised of subjects in the Safety population for whom at least one postprandial Triglyceride sample was obtained and analysed at baseline and post baseline.
 
	
 
Postprandial TG
 

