**8.2.1.1. Postprandial Triglyceride Evaluation**

[figure not shown]
Each subject will undergo, at pre-dose and post-dose, a fat meal challenge, consisting of 30% fat by calories, to be consumed within 15 min ( $\pm 10$  min). Triglyceride (TG) measurements will be collected from 1 hour prior to the meal through 10 hours after the meal (at meal time and 1, 2, 3, 4, 5, 6, 7, 10 hours post-meal).

The following will be taken into consideration when pooling placebo data. For all dosing with only a single dose administered at 0h, two doses at 0h and 4h, and hourly dosing starting 0h x 9 doses, only one meal was provided within the TG assessment period (Part 1, Cohorts 1, 2, 3, 4, 5, 6, 7, 10, and 11). For all dosing with two doses administered at 0h and 16h, a second meal with 20% fat was provided at 6h post-dose (Part 1, Cohort 8, and Part 2, Cohorts 1, 2, and 3). The second meal will impact the TG data beyond 6h and these cohorts data should be pooled separately from the single-meal placebo data. For only the TG analysis the pooled placebo in Part 1 will not include Cohort 8; placebo data in cohort 8 will be displayed separately.

For subjects undergoing a dosing regimen, the post-dose meal will start 2 hours post-dose. The first TG measurement will be collected 1 hour post-dose which is 1 hour pre-meal, and TG collections will run through 12 hours post-dose.

To serve as a baseline comparator, the same TG profile will be collected prior to dosing, also in the morning. This will be the day prior to morning dosing, for subjects undergoing a morning dosing regimen. Please see the following figure for further information on the exact dosing:

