**8.2.1.2. Postprandial Triglyceride AUC**

Postprandial triglyceride AUC(1-12) and AUC(2-5) (on day -1 and day 1 in part 1; day -1 day 1, and day 14 in part 2) will be calculated using trapezoidal rule.

Postprandial triglyceride AUC(1-12) and AUC(2-5) (on day 1 in part 1; day 1 and day 14 in part 2) will be calculated by adding the correction value in Section 8.2.1.1 to each time point after post-dose, but these adjustments/transformations will not apply to TG value at baseline day -1. Corrected TG AUC values will be also calculated using the linear trapezoidal rule.

Table and Figure will be produced for TG AUC and corrected TG AUC above of postprandial triglyceride by part, treatment, and day.

Table and Figure will be also produced for percent (%) change from baseline (e.g. Part 1: (Day 1 and Day -1 difference) / TG AUC on Day -1 ; Part 2: (Day 1 and Day -1 difference) / TG AUC on Day -1 as well as (Day 14 and Day -1 difference) / TG AUC on Day -1) in AUC and correct AUC of postprandial triglyceride by part and treatment.

Listing of individual change from baseline in AUC and Corrected AUC of postprandial triglyceride will be produced for both parts combined together.

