## 11.7. Appendix 7: Premature Withdrawals & Handling of Missing Data

### 11.7.1. Premature Withdrawals

Element	Reporting Detail
General	
 
• Subject study completion is defined in the protocol (Section 4.6) as completing all phases of the study including the follow-up visit. The end of the study is defined as the last subject's last visit.
 
• A subject may withdraw from study treatment at any time at his/her own request, or may be withdrawn at any time at the discretion of the investigator for safety, behavioural or administrative reasons. If a subject withdraws from the study, he/she may request destruction of any samples taken, and the investigator must document this in the site study records. If applicable, the reason for withdrawal of consent. A withdrawn subject may be replaced with another subject who will be assigned to the same treatment randomization. If a subject withdraws from the study, he/she may request destruction of any samples taken, and the investigator must document this in the site study records. Additional subjects/cohorts may be enrolled to allow for evaluation of additional dose levels. All available data from subjects who were withdrawn from the study will be listed and all available planned data will be included in summary tables and figures, unless otherwise specified.
 

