**11.7.2.3. Handling of Missing Data for Statistical Analysis**

Element	Reporting Detail
Imputation	

• No imputation will be carried out for any parameters

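### The SAP's missing-data rule for corrected triglyceride is triggered by samples that do not enter the correction, so one irrelevant lost tube can void a subject's corrected profile and AUCs for that day

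*SAP*

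**What the plan says.** SAP 8.2.1.1 shifts every post-dose TG value by a constant so that the pre-meal levels of the two days agree. For Day 1 the constant is "Day -1 (1hr + 2hr)/2) – (Day 1 (1hr + 2hr)/2", and Part 2 has a parallel formula for Day 14. SAP 8.2.1.2 says the corrected AUC(1-12) and AUC(2-5) "will be calculated by adding the correction value in Section 8.2.1.1 to each time point after post-dose", using the linear trapezoidal rule.

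The derivation table in SAP 11.5.2.2 gives this correction its own missing-data entry: "Missing if any TG value is missing for either post dose or pre-dose at any time point".

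Four other provisions bear on it:
- SAP 11.7.2.3: "No imputation will be carried out for any parameters".
- SAP 11.3.2, notes: "any evaluation which is closer to an adjacent (nominal) time than to its own nominal sampling will not be used". A badly mistimed sample therefore also becomes a missing one.
- SAP 11.7.1, on withdrawn subjects: "all available planned data will be included in summary tables and figures, unless otherwise specified". This gives way wherever a specific rule exists.
- SAP Section 4: the PD population takes Safety subjects "for whom at least one postprandial Triglyceride sample was obtained and analysed at baseline and post baseline". An affected subject therefore stays in the population.

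No section says how a TG AUC, corrected or not, treats a missing point.

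**The concern.** The entry is wider than the derivation it belongs to. The correction is built from pre-meal values, but the words extend to every sample on both days. A programmer who follows them would blank the whole corrected profile, and with it both corrected AUCs, because of a late sample that the correction never uses.

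Three features of the plan make this matter more:
- Cohorts in Parts 1 and 2 have 6 active and 2 placebo subjects (protocol 3.2). For TG, the Part 1 Cohort 8 placebo is shown on its own (SAP 8.2.1.1), so one lost tube there leaves one subject.
- In Part 1 Cohort 8 and all of Part 2, SAP 8.2.1.1 says a second meal affects TG beyond 6h. A missing late sample, from the stretch already regarded as affected, would remove the unaffected AUC(2-5).
- The programming note for Tables 5.7 and 5.8 (SAP Appendix 12) removes the count columns from the percent-change summaries, so a reader of those tables would not see the loss.

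**Working it through.** The plan states no figure on this point, so there is none to reproduce.

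**Sample count.** SAP 8.2.1.1 takes one sample 1h before the meal and then samples "at meal time and 1, 2, 3, 4, 5, 6, 7, 10 hours post-meal". That is 1 + 1 + 8 = 10 per profile, at 1, 2, 3, 4, 5, 6, 7, 8, 9 and 12h relative to dosing. A Day -1/post-dose pair has 2 × 10 = 20.

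**Samples each quantity needs:**
- Correction: 1h and 2h on both days, so 4. The other 20 − 4 = 16 do not enter it.
- Percent change in corrected AUC(2-5), with no gaps allowed: 2, 3, 4 and 5h on both days, plus the 1h values for the correction, so 2 × 5 = 10.
- Percent change in corrected AUC(1-12), with no gaps allowed: all 20.
- The rule read literally, for any corrected quantity: all 20.

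**Chance that a subject loses the result.** The documents give no per-sample missing rate. I assume a rate p, independent across samples, and show a range. The loss is 1 − (1 − p)^k for k required samples. For example, at p = 2%: 1 − 0.98^20 = 33.2%, 1 − 0.98^10 = 18.3% and 1 − 0.98^4 = 7.8%.

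| Assumed p | Literal rule, k = 20 | AUC(2-5) percent change, k = 10 | Correction only, k = 4 |
|---|---|---|---|
| 1% | 18.2% | 9.6% | 3.9% |
| 2% | 33.2% | 18.3% | 7.8% |
| 5% | 64.2% | 40.1% | 18.5% |

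**Per cohort of 6 active subjects.** The expected number lost is 6 times the per-subject loss. Under the literal rule it is 1.09, 1.99 and 3.85 at 1%, 2% and 5%. For AUC(2-5) percent change on its own inputs it is 0.57, 1.10 and 2.41. The chance that at least one of the six is lost, 1 − (1 − loss)^6, is 70%, 91% and 99.8% under the literal rule, against 45%, 70% and 95% for AUC(2-5) on its own inputs.

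**Across days in Part 2.** The entry does not say whether its reach stops at one post-dose day. If it spanned Day -1, Day 1 and Day 14, k would be 30 and the loss 26.0%, 45.5% and 78.5%. Part 2 Cohort 1 stopped dosing before Day 7 (SAP 2.2) and has no Day 14 profile, so it would then lose its Day 1 corrected results too. The separate Day 1 and Day 14 formulas point to a per-day reading, which the table uses, but the text leaves it open.

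**The case against.** The strongest reply is that the sentence is loose rather than wrong. Other rows of the table tie missingness to their own inputs, and the correction is applied at each nominal time point. Read in that spirit, the entry could mean any value that enters the derivation. That intent is possible. But the other rows name their inputs, whereas this one reaches to any time point, and the available-data provision in SAP 11.7.1 yields to a specific rule. Nothing overrides the literal reading, so the text needs settling either way.

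Second, the stakes are limited. Postprandial TG is a secondary endpoint, summarised descriptively with no hypothesis test. The PK/PD modelling is not being performed, and the SAP was written after Part 3 was not initiated. This stands and lowers the severity.

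Third, the size is hypothetical. TG sampling is done during inpatient stays, so 5% per tube is harsh. If missed tubes cluster within subjects, fewer subjects are lost for the same rate. The 4-sample comparison describes the correction, not a corrected AUC, and a complete AUC(1-12) on both days needs all 20 samples under any rule. All of this stands. Requiring complete profiles is a defensible choice for AUC(1-12), but it does not justify voiding AUC(2-5) for a 12h tube.

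A reader might also infer that corrected AUC is the only percent-change AUC to be plotted, because the titles of Figures 5.9 and 5.10 refer to corrected values. SAP 8.2.1.2 plans a figure for both versions, so this does not hold.

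**Conclusion.** Followed literally, SAP 11.5.2.2 discards corrected TG results that could be computed: 16 of the 20 samples in a pair can void a correction they do not enter. The fair measure of avoidable loss is AUC(2-5) percent change. At an assumed 2% per sample, 33% of subjects would be lost instead of 18%, or about 2.0 instead of 1.1 of 6 actives. AUC(1-12) gains only if a gap rule is added. These sizes rest on assumed, independent missing rates and on a per-day reading of the rule.

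The effect is confined to corrected TG, corrected AUC(1-12) and AUC(2-5), and their percent change. Uncorrected TG and AUC and the PD population are untouched.

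It may be tempting to infer that the rule selects subjects by gastrointestinal tolerability. The documents do not say that subjects with such events miss TG draws. The documented problem, in Part 2 Cohort 1, was early stopping, which leaves Day 14 unevaluable under any rule.

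Severity is minor to moderate: a descriptive secondary PD endpoint, but with small cohorts and an easy remedy.

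**What to change.** Replace the missing-data entry for the TG correction in SAP 11.5.2.2 with three statements, each applied within one post-dose day:
1. The correction is missing only if one of its own 1h or 2h inputs, on Day -1 or on that post-dose day, is missing.
2. The corrected TG at time t is missing only if the correction, or the post-dose TG at t, is missing.
3. Each corrected AUC is set to missing according only to the correction and the samples inside its own window. The sponsor states how many interior gaps are tolerated.

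The gap tolerance is for the sponsor to choose. Requiring only the window's end points would let AUC(2-5) rest on the 2h and 5h values alone, which could miss the early excursion. Using a single pre-meal value when its partner is missing should not be added: it alters the prespecified correction and sits uneasily with the no-imputation rule in SAP 11.7.2.3.

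The cost is a few sentences in the SAP and a small programming change. No new data are needed.
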